4.2.4. Dose Escalation Decisions and Determination of MTD

4.2.4.1. Dose-Limiting Toxicity

An event is considered to be a dose-limiting toxicity (DLT) if the event occurs within the first 21 days of treatment and meets the criteria listed in Table 1, unless it can be clearly established that the event is unrelated to treatment.

Toxicity	DLT Definition
Hematologic	 Grade 3 neutropenia (absolute neutrophil count [ANC] <1000/mm³) for ≥5 days or Grade 4 neutropenia of any duration Grade 3 or greater febrile neutropenia Grade 4 or greater anemia of any duration Grade 4 thrombocytopenia (platelets <25,000/mm³), or Grade 3 thrombocytopenia with bleeding
Non-hematologic	 Alanine aminotransferase (ALT) >3x upper limit of normal (ULN) + bilirubin ≥2xULN (>35% direct) or ALT between 3-5 X ULN with bilirubin < 2xULN but with hepatitis symptoms^a or rash (See Section 5.4.5 for Liver Stopping Criteria) Grade 3 nausea, vomiting or diarrhea that does not improve within 72h despite appropriate supportive treatment(s) Grade 4 or greater nausea, vomiting, or diarrhea Grade 3 hypertension^b (uncontrolled despite addition of up to 2 antihypertensive medications) Grade 4 or greater clinically significant non-hematologic toxicity per National Cancer Institute - Common Terminology Criteria for Adverse Events (NCI- CTCAE), v4 except toxicities listed in Section 4.2.4.2.
Other	 Inability to receive at least 80% of scheduled doses in the DLT observation period due to toxicity^c Grade 2 or higher toxicity that occurs beyond 21 days which in the judgment of the investigator and GlaxoSmithKline (GSK) Medical Monitor is considered to be a DLT

 Table 1
 Dose-Limiting Toxicity Criteria

Toxicity Grading based on NCI-CTCAE v4

a. New or worsening symptoms believed to be related to liver injury (such as fatigue, nausea, vomiting, right upper quadrant pain or tenderness, or jaundice) or believed to be related to hypersensitivity (such as fever, rash or eosinophilia)

- b. Grade 3 hypertension adequately controlled by antihypertensive medication(s) is not considered to be a DLT.
- c. Subjects unable to receive at least 80% of scheduled doses for reasons other than toxicity (e.g., acute illness, disease progression) will not be evaluable for DLT purposes and will be replaced in the cohort

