4. ANALYSIS POPULATIONS

4.1. List of Populations

Population	Definition / Criteria	Analyses Evaluated
Screened	All participants who were screened for eligibility	Study Population
Enrolled	All participants who signed the ICF	Study Population
All Treated	Defined as all subjects who receive at least one dose of GSK3326595.	Safety Anti-cancer activity Efficacy (final analysis)
All Evaluable	For Part 1: Defined as subjects who have had any post-baseline response data, or who discontinued without any response data collected. For Part 2: Defined as subjects who have had	Interim Analysis
	two post baseline disease assessments, have progressed or died, or permanently discontinued from the study treatment for mTCC, TNBC, ER+BC, HPV+, NHL and NSCLC cohorts. It is defined as subjects who have had three post baseline disease assessments, have progressed or died, or permanently discontinued from the study treatment for ACC and GBM cohorts.	

Table 7Analysis Populations

Population	Definition / Criteria	Analyses Evaluated
Pharmacokinetic (PK)	Consist of all subjects from the All Treated Population for whom a PK sample is obtained and analyzed. Note: PK samples that may be affected by protocol deviations will be reviewed by the study team to determine whether or not the sample will be excluded.	PK
Pharmacodynamic (PD)	Defined as subjects in the All Treated Subjects Population for whom paired and evaluable tumor biopsies (pre- and on- treatment time points) or plasma or urine were obtained and analyzed for biomarkers.	PD

Refer to Appendix 12: List of Data Displays which details the population used for each display. Note that for the interim analyses, the All Evaluable population will be used for efficacy analyses, and the All-Treated Population will be used for safety analyses. However, for the final analysis, the All Treated Population will be used for all displays.

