5.1.1. Treatment Display

The actual treatment of a subject will be derived from exposure data. The first dose the subject received will be used as actual treatment. Scheduled (planned) treatment is collected on dosing regimen eCRF page. Efficacy, safety and PK analysis will be based on the All Treated Population.

Per Protocol Amendment 7, if the GSK3326595 tablet bioavailability is comparable to that of the GSK3326595 capsules from Part 1 Food Effect and Relative Bioavailability Sub-study, all new and ongoing subjects may be switched from capsules to tablets for the remainder of the study, once they have been notified by the Sponsor. As of 3 Nov 2021, per GSK communication, tablet and capsule cohorts within the same disease/dosage groups will be combined.

The leading dose formulation (tablet or capsule) and the leading dose level are specified in treatment.

- For Part 1 dose escalation cohorts, all data will be pooled and descriptive analyses summarized and listed by investigated GSK3326595 dose under QD dose escalation cohort or BID dose escalation cohort. PK/PD expansion cohorts will be summarized together with dose escalation cohorts dose level. If applicable, Part 1 Food Effect Relative Bioavailability Sub-study data will also be included in Part 1 summary tables as a separate column. The treatment groups for Part 1 are:
 - Part 1 QD Dose GSK3326595 12.5 mg Capsule
 - Part 1 QD Dose GSK3326595 25 mg Capsule
 - Part 1 QD Dose GSK3326595 50 mg Capsule
 - Part 1 QD Dose GSK3326595 100 mg Capsule
 - Part 1 QD Dose GSK3326595 200 mg Capsule
 - Part 1 QD Dose GSK3326595 300 mg Capsule
 - Part 1 QD Dose GSK3326595 400 mg Capsule
 - Part 1 QD Dose GSK3326595 600 mg Capsule
 - Part 1 BID Dose GSK3326595 50 mg Capsule
 - Part 1 BID Dose GSK3326595 100 mg Capsule
 - Part 1 BID Dose GSK3326595 150 mg Capsule
 - Part 1 BID Dose GSK3326595 200 mg Capsule
 - Food Effect and Relative Bioavailability Sub-study 300mg QD (apply to table/figures)
 - Part 1 Food Effect 300mg Sequence 1 (Tablet Fasted Tablet Fed Capsule Fasted) (apply to listings)
 - Part 1 Food Effect 300mg Sequence 2 (Tablet Fed Tablet Fasted Capsule Fasted) (apply to listings)
- For Part 2 dose expansion cohorts, data will be summarized and listed by cohorts. The treatment groups for Part 2 are:
 - Part 2 TNBC 400mg QD Capsule Cohort

- Part 2 mTCC 400mg QD Capsule Cohort
- Part 2 GBM 400mg QD Capsule Cohort
- Part 2 ER+BC 400mg QD Capsule Cohort
- Part 2 HPV+ 400mg QD Capsule Cohort

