- Part 2 ACC 400mg QD Capsule Cohort
- Part 2 ACC 300mg QD Tablet Cohort
- Part 2 NHL P53 Mutant 400 mg QD Capsule
- Part 2 NHL P53 Mutant 300 mg QD Capsule
- Part 2 NHL P53 Mutant 300 mg QD Tablet (if applicable)
- Part 2 NHL P53 Wild Type 400 mg QD Capsule
- Part 2 NHL P53 Wild Type 300 mg QD Capsule
- Part 2 NHL P53 Wild Type 300 mg QD Tablet (if applicable)
- Part 2 NHL P53 Unknown 400 mg QD Capsule
- Part 2 NHL P53 Unknown 300 mg QD Capsule
- Part 2 NHL P53 Unknown 300 mg QD Tablet (if applicable)
- Part 2 NSCLC 300 mg QD Capsule
- Part 2 NSCLC 300 mg QD Tablet (if applicable)
- Part 2 ACC TN 300mg Tablet Cohort

NB 1: NHL P53 status is based on central lab data. If the central lab data is missing then the status will be considered Unknown.

NB 2: As per GSK communication, as of *3Nov2021 tablet and capsule cohorts within the same disease/dosage groups will be combined.*

For Part 3 combination dose escalation, some AE and exposure tables and listings will be displayed for GSK3326595 and pembrolizumab separately. All others will be summarized and listed by dose levels of both GSK3326595 plus pembrolizumab. (e.g., GSK3326595 100mg + pembrolizumab).

Subjects enrolled in Part 1, may be included in a Part 2 disease-specific cohort analyses (tables and figures) if the subjects were treated at the Part 2 dose expansion and have the same disease type as required for the cohort. These subjects will be provided in a separate listing as well. Additional safety tables, may be provided for all subjects treated at the RP2D, regardless of the Part of the study to which they were enrolled.

Unless otherwise noted, the denominator for the percentage is the number of subjects in the analysis population used for that summary.

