All COVID-19 assessments and symptom assessments for subjects with COVID-19 adverse events will be summarized based on all recorded AEs. There will be no separate definition of "treatment-emergent" AEs.

All AEs will be listed. A listing of subject numbers for individual adverse events will be provided.

A listing of adverse events recorded as dose-limiting toxicities for Part 1 subjects will be provided. Additionally, a summary of the number of patients experiencing DLTs for Part 1 subjects will be provided.

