3.57	All Treated	ODMOD1	Summary of Dose Reductions of GSK3326595	ICH E3 Part 1 (by dose), Part 2 (by cohort), Part 1/Part 2 300mg/400mg/Total/Overall, Part 3 (by dose)	SAC
3.58	All Treated	ODMOD1	Summary of Dose Reductions of Pembrolizumab	Part 3	SAC
3.59	All Treated	ODMOD2	Summary of Dose Interruptions of GSK3326595	ICH E3 Part 1 (by dose), Part 2 (by cohort), Part 1/Part 2 300mg/400mg/Total/Overall, Part 3 (by dose)	SAC
3.60	All Treated	ODMOD3	Summary of Dose Delays of Pembrolizumab	Part 3	SAC
3.65	All Treated	AE1	Summary of Adverse Events Recorded as Dose-Limiting Toxicities by Preferred Term– Part 1	ICH E3 Part 1	SAC
ECOG	Performance				
3.66	All Treated	PS1A	Summary of ECOG Performance Status	ICH E3 Part 1 (by dose), Part 2 (by cohort), Part 1/Part 2 300mg/400mg/Total/Overall, Part 3 (by dose)	SAC
Ocular	Adverse Event	s			
3.70	All Treated	from IB 2022	Summary of Adverse Events (Ocular Events) by Preferred Term	Part 1, Part 2, Part 3, Part 1+2	SAC
3.72	All Treated	from IB 2022	Summary of Adverse Events (Bone- Related Events) by Preferred Term	Part 1, Part 2, Part 3, Part 1+2	SAC
Bone N	Aineral Density	Shifts			

		IDSL / Example			
No.	Population	Shell	Title	Programming Notes	Deliverable
3.75	All Treated	from IB 2022	Summary of Bone Mineral Density Shifts from Baseline Relative to Normal Range, Among Patients with Pre- Treatment Baseline DEXA Scan – Local Labs	Part 1, Part 2, Part 3, Part 1+2	SAC
3.77	All Treated	from IB 2022	Summary of Bone Mineral Density Shifts from Baseline Relative to Normal Range, Among Patients with First DEXA Scan Performed on Treatment – Local Labs	Part 1, Part 2, Part 3, Part 1+2	SAC

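### The SAP has no DLT-evaluable population, so Table 3.65 keeps subjects who cannot be assessed for DLT in its denominator

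*SAP*

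**What the plan says.** **Population.** SAP section 4.1 gives All Treated as "Defined as all subjects who receive at least one dose of GSK3326595". It adds that "for the final analysis, the All Treated Population will be used for all displays". The section also lists Screened, Enrolled, All Evaluable, PK and PD populations, but none for DLT.

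**Display.** SAP section 15.12.7 assigns Table 3.65, "Summary of Adverse Events Recorded as Dose-Limiting Toxicities by Preferred Term– Part 1", to All Treated. SAP section 8.1.1.2 promises a listing of DLTs and that "a summary of the number of patients experiencing DLTs for Part 1 subjects will be provided".

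**Denominator.** SAP section 5.1.1 states that, unless otherwise noted, "the denominator for the percentage is the number of subjects in the analysis population used for that summary". It assigns each subject to the first dose received. It also says that "PK/PD expansion cohorts will be summarized together with dose escalation cohorts dose level".

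**Evaluability.** Footnote c to Protocol Table 1 (section 4.2.4.1) says that subjects unable to receive at least 80% of scheduled doses for non-toxicity reasons "will not be evaluable for DLT purposes and will be replaced in the cohort". Protocol section 4.2.2 replaces subjects who do not receive more than 80%. Section 4.2 replaces anyone who stops therapy during the DLT period for a reason other than a DLT.

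**Role.** Protocol section 3 places DLTs among the Part 1 primary endpoints. Section 11.10.2.1.2 asks that they be listed, and summarized by dose cohort.

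**The concern.** A DLT proportion has meaning only among subjects who could have shown a DLT. The protocol recognises this: it sets an evaluability rule and replaces those who fail it. The SAP drops the rule when the proportion is reported. A replaced subject has had at least one dose and is therefore All Treated. The subject counts in the denominator but, by the protocol's rule, does not inform the DLT question.

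What is at stake is how the Part 1 DLT data are read. The SAP's introduction excepts the mTPI analysis from the analyses to be carried out under it, and Appendix 12 lists no mTPI display. The DLT-specific displays are Table 3.65 and Listing 61. Neither is planned to show DLT n/N by dose on evaluable subjects, so the report would not directly show the rates relevant to the dose decisions.

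**Working it through.** **1. The plan's own figure.** The documents give no DLT rate by dose. The one stated figure that depends on DLTs over subjects treated is the mTPI grid, Protocol Figure 4-1 (target 30%, epsilon 0.05 each side). Let F be the Beta(1 + x, 1 + n − x) distribution function for x DLTs in n subjects. The unit probability masses are:
- escalate: F(0.25)/0.25
- stay: [F(0.35) − F(0.25)]/0.10
- de-escalate: [1 − F(0.35)]/0.65

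The largest gives the decision, and U is added when 1 − F(0.30) > 0.95. The uniform prior and the 0.95 cut-off are assumptions; the documents state neither. All 195 cells in rows 0 to 6, up to n = 30, agree with the grid.

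**2. Effect of the denominator.** Take d DLTs among n evaluable subjects, and r replaced subjects without a recorded DLT.
- Evaluable rate: d/n
- Displayed rate: d/(n + r), never above d/n; the relative reduction is r/(n + r)

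No values of d, n or r by dose are in the documents. With n = 6 as an illustration:

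| DLTs | r = 0 | r = 1 | r = 2 |
|---|---|---|---|
| 1 | 1/6 = 16.7% | 1/7 = 14.3% | 1/8 = 12.5% |
| 2 | 2/6 = 33.3% | 2/7 = 28.6% | 2/8 = 25.0% |

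**3. An overall illustration.** Protocol section 4.2.3 expects about 38 subjects to complete the DLT period; sections 4.2.4.8 and 11.9.1 say about 42. If 38 of 42 were evaluable and the other 4 had no DLT, a 30% rate would show as 0.30 × 38/42 = 27.1%. This is an assumption, because both figures are described as completers.

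**4. The exception.** Protocol Table 1 allows an event after day 21 to be declared a DLT. If one of two replaced subjects had such an event, the display would be 3/8 = 37.5%, above the within-window 2/6 = 33.3%.

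**5. Expansion subjects.** Protocol Table 10 gives the expansion cohort the same Days 1–21 DLT observation period, and Table 1 does not restrict DLTs to escalation subjects. Adding 12 subjects with the same one-third rate gives (2 + 4)/(6 + 12) = 33.3%, unchanged. The figure falls to 2/18 = 11.1% only if none of the 12 has a DLT, and that would be the pooled estimate from assessed subjects.

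**6. Reading the grid.** One extra denominator subject can change the Figure 4-1 entry a reader looks up: 2/3 is D but 2/4 is S; 1/5 is S but 1/6 is E. This concerns a reader using Table 3.65. Nothing says the mTPI was run on All Treated.

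**The case against.** The SAP follows the protocol's general safety rule. Protocol section 11.9.5 evaluates safety on All Treated, and the protocol asks only for a DLT listing and a summary by dose cohort. Part 1 is descriptive, with no hypothesis tested. SAP section 8.1.1.2 promises a number of patients, not a rate. Listing 61 shows every DLT by dose and Listing 8 shows exposure, so the events and much of the dosing information are disclosed. The RP2D was chosen in March 2018 (Protocol section 4.3.2); SAP version 1.0 is dated September 2022.

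Much of this stands, and it limits the point to reporting. It does not remove it. Section 11.9.5 allows further populations to be defined in the analysis plan, and Table 1 gives DLTs their own evaluability rule. The percentage follows from the SAP's general denominator rule, and a bare count is hard to interpret without the evaluable N. The listings leave the reader to reapply the 80% rule subject by subject.

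A reader might go further and infer that pooling the expansion cohort understates the rate. The documents do not support that: those subjects have the same DLT window, and Protocol section 4.2.2 counts safety data from additional subjects at cleared doses toward the MTD.

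**Conclusion.** The point holds as a reporting defect in Table 3.65. Subjects the protocol calls not evaluable for DLT stay in the denominator of a Part 1 primary-endpoint display and, unless one has a late-declared DLT, can only lower the proportion. The conclusion assumes that percentages are shown under SAP section 5.1.1 and that at least one treated subject was replaced. The size cannot be computed; 33.3% becoming 28.6% or 25.0% is illustrative only.

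Two stronger readings are tempting and not supported:
- **Net understatement at every dose.** Late-declared DLTs add to the numerator. Assignment by first dose can place a DLT that follows intra-subject escalation (Protocol section 4.2.4.7) in the column of the lower starting dose. The net direction by dose is not established.
- **An effect on dose escalation or the MTD.** The mTPI analysis lies outside the analyses executed under the SAP, replacement of non-evaluable subjects operates regardless of Table 3.65, and the RP2D predates the SAP.

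**What to change.** - **Reconcile the rule first.** Protocol section 4.2.2 (more than 80%) and Table 1 (at least 80%) differ for a subject at exactly 80%, and section 4.2 words replacement differently again. The sponsor should settle which wording governs evaluability.
- **Add a DLT-evaluable population to SAP section 4.1:** Part 1 subjects who had a DLT, or who completed the 21-day period and met the reconciled dosing rule.
- **Change Table 3.65** to show DLT n/N by dose on that population, and flag DLTs declared after day 21.
- **Keep All Treated** for the other safety displays, and word the final-analysis sentence in section 4.1 to allow the exception.

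The cost is one population definition, one subject-level flag derived from dosing and DLT records already collected, and one table denominator. Showing escalation and expansion subjects separately would aid reading but is optional. The 38 and 42 expected DLT-period completers in the protocol should be reconciled at the same time.

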4.2. Protocol Deviations

Important protocol deviations (including deviations related to study inclusion/exclusion criteria, conduct of the trial, patient management or patient assessment) will be summarized and listed.

Separately, important deviations which result in exclusion from analysis populations and events that result in exclusion from analysis populations will be summarized and listed, if there are any.

Protocol deviations will be tracked by the study team throughout the conduct of the study in accordance with the Protocol Deviation Management Plan.

- Data will be reviewed prior to freezing the database to ensure all important deviations are captured and categorized on the protocol deviations dataset.
- This dataset will be the basis for the summaries and listings of protocol deviations.

A separate listing of all inclusion/exclusion criteria deviations will also be provided. This listing will be based on data as recorded on the inclusion/exclusion page of the eCRF.

5. CONSIDERATIONS FOR DATA ANALYSES AND DATA HANDLING CONVENTIONS

5.1. Study Treatment & Sub-group Display Descriptors

All data within scheduled visits up to the time of study completion/withdrawal from study will be included in the analysis summaries, regardless of duration of treatment. Unscheduled visits will be considered for most extreme result reporting (e.g., worst grade post-baseline, response assessments for ORR), and included in data listings.

5.1.1. Treatment Display

The actual treatment of a subject will be derived from exposure data. The first dose the subject received will be used as actual treatment. Scheduled (planned) treatment is collected on dosing regimen eCRF page. Efficacy, safety and PK analysis will be based on the All Treated Population.

Per Protocol Amendment 7, if the GSK3326595 tablet bioavailability is comparable to that of the GSK3326595 capsules from Part 1 Food Effect and Relative Bioavailability Sub-study, all new and ongoing subjects may be switched from capsules to tablets for the remainder of the study, once they have been notified by the Sponsor. As of 3 Nov 2021, per GSK communication, tablet and capsule cohorts within the same disease/dosage groups will be combined.

The leading dose formulation (tablet or capsule) and the leading dose level are specified in treatment.

- For Part 1 dose escalation cohorts, all data will be pooled and descriptive analyses summarized and listed by investigated GSK3326595 dose under QD dose escalation cohort or BID dose escalation cohort. PK/PD expansion cohorts will be summarized together with dose escalation cohorts dose level. If applicable, Part 1 Food Effect Relative Bioavailability Sub-study data will also be included in Part 1 summary tables as a separate column. The treatment groups for Part 1 are:
 - Part 1 QD Dose GSK3326595 12.5 mg Capsule
 - Part 1 QD Dose GSK3326595 25 mg Capsule
 - Part 1 QD Dose GSK3326595 50 mg Capsule
 - Part 1 QD Dose GSK3326595 100 mg Capsule
 - Part 1 QD Dose GSK3326595 200 mg Capsule
 - Part 1 QD Dose GSK3326595 300 mg Capsule
 - Part 1 QD Dose GSK3326595 400 mg Capsule
 - Part 1 QD Dose GSK3326595 600 mg Capsule
 - Part 1 BID Dose GSK3326595 50 mg Capsule
 - Part 1 BID Dose GSK3326595 100 mg Capsule
 - Part 1 BID Dose GSK3326595 150 mg Capsule
 - Part 1 BID Dose GSK3326595 200 mg Capsule
 - Food Effect and Relative Bioavailability Sub-study 300mg QD (apply to table/figures)
 - Part 1 Food Effect 300mg Sequence 1 (Tablet Fasted Tablet Fed Capsule Fasted) (apply to listings)
 - Part 1 Food Effect 300mg Sequence 2 (Tablet Fed Tablet Fasted Capsule Fasted) (apply to listings)
- For Part 2 dose expansion cohorts, data will be summarized and listed by cohorts. The treatment groups for Part 2 are:
 - Part 2 TNBC 400mg QD Capsule Cohort

- Part 2 mTCC 400mg QD Capsule Cohort
- Part 2 GBM 400mg QD Capsule Cohort
- Part 2 ER+BC 400mg QD Capsule Cohort
- Part 2 HPV+ 400mg QD Capsule Cohort
- Part 2 ACC 400mg QD Capsule Cohort
- Part 2 ACC 300mg QD Tablet Cohort
- Part 2 NHL P53 Mutant 400 mg QD Capsule
- Part 2 NHL P53 Mutant 300 mg QD Capsule
- Part 2 NHL P53 Mutant 300 mg QD Tablet (if applicable)
- Part 2 NHL P53 Wild Type 400 mg QD Capsule
- Part 2 NHL P53 Wild Type 300 mg QD Capsule
- Part 2 NHL P53 Wild Type 300 mg QD Tablet (if applicable)
- Part 2 NHL P53 Unknown 400 mg QD Capsule
- Part 2 NHL P53 Unknown 300 mg QD Capsule
- Part 2 NHL P53 Unknown 300 mg QD Tablet (if applicable)
- Part 2 NSCLC 300 mg QD Capsule
- Part 2 NSCLC 300 mg QD Tablet (if applicable)
- Part 2 ACC TN 300mg Tablet Cohort

NB 1: NHL P53 status is based on central lab data. If the central lab data is missing then the status will be considered Unknown.

NB 2: As per GSK communication, as of *3Nov2021 tablet and capsule cohorts within the same disease/dosage groups will be combined.*

For Part 3 combination dose escalation, some AE and exposure tables and listings will be displayed for GSK3326595 and pembrolizumab separately. All others will be summarized and listed by dose levels of both GSK3326595 plus pembrolizumab. (e.g., GSK3326595 100mg + pembrolizumab).

Subjects enrolled in Part 1, may be included in a Part 2 disease-specific cohort analyses (tables and figures) if the subjects were treated at the Part 2 dose expansion and have the same disease type as required for the cohort. These subjects will be provided in a separate listing as well. Additional safety tables, may be provided for all subjects treated at the RP2D, regardless of the Part of the study to which they were enrolled.

Unless otherwise noted, the denominator for the percentage is the number of subjects in the analysis population used for that summary.

